#### 5.4.3. Management of Immune-Related Adverse Events

Immuno-oncology agents such as GS-4224 are associated with irAEs. Early recognition and management of irAEs may mitigate severe toxicity. Investigators should also monitor subjects closely for potential irAEs, which may manifest after weeks of treatment, at the earliest. Such events may consist of persistent rash, diarrhea, colitis, autoimmune hepatitis, pneumonitis, encephalitis, arthritis, glomerulonephritis, cardiomyopathy, or uveitis and other inflammatory eye conditions.

Management algorithms have been developed to assist investigators in assessing and managing the following groups of irAEs: GI, pulmonary, dermatological, renal, hepatic, neurological, and endocrine, among others.

AEs (both non-serious and serious) associated with drug exposure and consistent with an immune phenomenon may represent an immunologic etiology. These irAEs may be predicted based on the nature of the study drugs, their mechanism of action, and reported experience with immunotherapies that have a similar mechanism of action. An irAE can occur any time from shortly after the first dose to several months after the last dose of treatment. Particular attention should be paid to AEs that may be suggestive of potential irAEs, as outlined below.

#### 5.4.4. Dermatological irAEs

Rule out non-inflammatory causes. If non-inflammatory cause is identified, treat accordingly and continue therapy per protocol.

**Table 5-1. Dermatological irAE Management Algorithm**

Dermatological irAEs		
CTCAE Grade of Rash	Management	Follow Up
Grade 1-2 Covering ≤ 30% body surface area	Symptomatic therapy (eg, antihistamines, topical corticosteroids). Continue GS-4224 therapy per protocol.	If persists > 1 to 2 weeks or recurs: Consider skin biopsy. Delay GS-4224 therapy. Consider 0.5-1 mg/kg/day methylprednisolone IV or oral equivalent. Once improving, taper corticosteroids over ≥ 1 month; consider prophylactic antibiotics for opportunistic infections; and resume GS-4224 therapy per protocol. If worsens: Treat as Grade 3-4.
Grade 3-4 Covering > 30% body surface area; life-threatening consequences	Interrupt or discontinue GS-4224 therapy per protocol. Consider skin biopsy. Dermatology consult 1-2 mg/kg/day methylprednisolone IV or IV equivalent.	If improves to Grade 1: Taper corticosteroids over ≥ 1 month; add prophylactic antibiotics for opportunistic infections. Resume GS-4224 therapy per protocol.

CTCAE Common Terminology Criteria for Adverse Events; irAE immune related adverse event; IV intravenous(ly)

#### 5.4.5. Gastrointestinal (GI) irAEs

Rule out non-inflammatory causes. If non-inflammatory cause is identified, treat accordingly and continue therapy. Opiates/narcotics may mask symptoms of perforation. Infliximab should not be used in cases of perforation or sepsis.

**Table 5-2. Gastrointestinal (GI) irAE Management Algorithm**

Gastrointestinal (GI) irAEs		
CTCAE Grade of Diarrhea/Colitis	Management	Follow Up

Grade 1                      Diarrhea: < 4 stools/day over baseline.                      Colitis: asymptomatic.
	
Continue GS-4224 therapy per protocol.                      Symptomatic treatment.
	
Close monitoring for worsening symptoms.                      Educate subject to report worsening immediately.                      Consider symptomatic treatment including hydration, electrolyte replacement, dietary changes (eg, American Dietetic Association colitis diet), and loperamide.  If worsens: Treat as Grade 2 or 3-4.

Grade 2                      Diarrhea: 4-6 stools per day over baseline; IV fluids indicated < 24 h; not interfering with activities of daily living (ADL).                      Colitis: abdominal pain; blood in stool.
	
Interrupt GS-4224 therapy per protocol.                      Symptomatic treatment.
	
If improves to Grade 1: Resume GS-4224 therapy per protocol.  If persists > 5 to 7 days or recurs: 0.5-1 mg/kg/day methylprednisolone or equivalent.                      When symptoms improve to Grade 1, taper corticosteroids over <math>\geq 1</math> month; consider prophylactic antibiotics for opportunistic infections; resume GS-4224 therapy per protocol.  If worsens or persists > 3 to 5 days with oral corticosteroids: Treat as Grade 3-4.

Grade 3-4                      Diarrhea (Grade 3): <math>\geq 7</math> stools per day over baseline; incontinence; IV fluids <math>\geq 24</math> h; interfering with ADL.                      Colitis (Grade 3): severe abdominal pain, medical intervention indicated, peritoneal signs.                      Grade 4: life-threatening, perforation
	
Discontinue GS-4224 therapy per protocol.                      1-2 mg/kg/day methylprednisolone IV or equivalent.                      Add prophylactic antibiotics for opportunistic infections.                      Consider lower endoscopy.
	
If improves: Continue corticosteroids until Grade 1, then taper over <math>\geq 1</math> month.  If persists > 3 to 5 days or recurs after improvement: Add infliximab 5 mg/kg (if no contraindication).  Note: Infliximab should not be used in cases of perforation or sepsis.

ADL activities of daily living; CTCAE Common Terminology Criteria for Adverse Events; irAE immune related adverse event; IV intravenous(ly)

**5.4.6. Pulmonary irAEs**

Rule out non-inflammatory causes. If non-inflammatory cause is identified, treat accordingly and continue therapy per protocol. Evaluate with imaging and pulmonary consultation.

**Table 5-3. Pulmonary irAE Management Algorithm**

Pulmonary irAEs		
CTCAE Grade of Pneumonitis	Management	Follow Up
Grade 1 Radiographic changes only.	Consider interruption of GS-4224 therapy per protocol. Monitor for symptoms every 2-3 days. Consider pulmonary and infectious disease consults.	Re-image every $\geq 3$ weeks. If worsens: Treat as Grade 2 or Grade 3-4.
Grade 2 Mild to moderate new symptoms	Interrupt GS-4224 therapy per protocol. Pulmonary and infectious disease consults. Monitor symptoms daily; consider hospitalization. 1 mg/kg/day methylprednisolone IV or oral equivalent. Consider bronchoscopy, lung biopsy.	Re-image every 1-3 days. If improves: When symptoms return to near baseline, taper corticosteroids over $\geq 1$ month, then resume GS-4224 therapy per protocol, and consider prophylactic antibiotics. If not improving after 2 weeks or worsening: Treat as Grade 3-4.
Grade 3-4 Severe new symptoms; new/worsening hypoxia; life-threatening.	Discontinue GS-4224 therapy per protocol. Hospitalize. Pulmonary and infectious disease consults. 2-4 mg/kg/day methylprednisolone IV or IV equivalent. Add prophylactic antibiotics for opportunistic infections. Consider bronchoscopy, lung biopsy.	If improves to baseline: Taper corticosteroids over $\geq 6$ weeks. If not improving after 48 h or worsening: Add additional immunosuppression (eg, infliximab, cyclophosphamide, IV immunoglobulin, mycophenolate mofetil).

CTCAE Common Terminology Criteria for Adverse Events; irAE immune related adverse event; IV intravenous(ly)

### 5.4.7. Hepatic irAEs

Rule out non-inflammatory causes. If non-inflammatory cause is identified, treat accordingly and continue therapy per protocol. Consider imaging for obstruction.

**Table 5-4. Hepatic irAE Management Algorithm**

Hepatic irAEs		
CTCAE Grade of Liver Test Elevation	Management	Follow Up
Grade 1 AST or ALT > ULN to 3 × ULN or total bilirubin > ULN to 1.5 × ULN	Continue GS-4224 therapy per protocol	Continue liver function tests (LFT) monitoring per protocol. If worsens: Treat as Grade 2 or Grade 3-4.
Grade 2 AST or ALT > 3 to ≤ 5 × ULN or total bilirubin > 1.5 to ≤ 3 × ULN	Interrupt GS-4224 therapy per protocol Increase frequency of monitoring to every 3 days If subject has concurrent AST or ALT > 3 × ULN and total bilirubin > 2 × ULN, discontinue GS-4224 therapy per protocol.	If returns to baseline: Resume routine monitoring; resume GS-4224 therapy per protocol. If elevations persist > 5 to 7 days or worsen: 0.5-1 mg/kg/day methylprednisolone IV or oral equivalent. When LFT returns to Grade 1 or baseline, taper corticosteroids over ≥ 1 month, consider prophylactic antibiotics for opportunistic infections, and resume GS-4224 therapy per protocol.
Grade 3-4 AST or ALT > 5 × ULN and/or total bilirubin > 3 × ULN.	Discontinue GS-4224 therapy per protocol Increase frequency of monitoring to every 1-2 days 1-2 mg/kg/day methylprednisolone IV or oral equivalent.* Add prophylactic antibiotics for opportunistic infections Consult gastroenterology Consider obtaining MRI/CT scan of liver and liver biopsy if clinically warranted	If returns to Grade 2: Taper corticosteroids over ≥ 1 month. If does not improve in > 3 to 5 days, worsens or rebounds: Add mycophenolate mofetil 1 g twice daily. If no response within an additional 3-5 days, consider other immunosuppressants per local guidelines.

\* The recommended starting dose for Grade 4 hepatitis is 2 mg/kg/day methylprednisolone IV.  
 ALT alanine aminotransferase; AST aspartate aminotransferase; CT computed tomography; CTCAE Common Terminology Criteria for Adverse Events; irAE immune related adverse event; IV intravenous(ly); LFT liver function test; MRI magnetic resonance imaging; ULN upper limit of normal

**5.4.8. Endocrine irAEs**

Rule out non-inflammatory causes. If non-inflammatory cause is identified, treat accordingly and continue therapy per protocol. Consider visual field testing, endocrinology consultation, and imaging.

**Table 5-5. Endocrine irAE Management Algorithm**

Endocrine irAEs		
Endocrine Disorder	Management	Follow Up
Asymptomatic TSH abnormality	Continue GS-4224 therapy per protocol. If TSH < 0.5 × lower limit of normal (LLN) or TSH > 2 × ULN, or consistently out of range in 2 subsequent measurements: Include free thyroxine at subsequent cycles as clinically indicated; consider endocrinology consult.	
Symptomatic endocrinopathy	Evaluate endocrine function. Consider pituitary scan. Symptomatic with abnormal lab/pituitary scan: Interrupt GS-4224 therapy per protocol; 1-2 mg/kg/day methylprednisolone IV or oral equivalent; initiate appropriate hormone therapy No abnormal lab/pituitary MRI scan but symptoms persist: Repeat labs in 1-3 weeks, MRI in 1 month.	If improves (with or without hormone replacement): Taper corticosteroids over ≥ 1 month and consider prophylactic antibiotics for opportunistic infections. Resume GS-4224 therapy per protocol. Subjects with adrenal insufficiency may need to continue corticosteroids with mineralocorticoid component.
Suspicion of adrenal crisis (eg, severe dehydration, hypotension, shock out of proportion to current illness)	Interrupt or discontinue GS-4224 therapy per protocol Rule out sepsis Stress dose of IV corticosteroids with mineralocorticoid activity IV fluids Consult endocrinologist If adrenal crisis ruled out, treat as above for symptomatic endocrinopathy	

irAE immune related adverse event; IV intravenous(ly); LLN lower limit of normal; MRI magnetic resonance imaging; TSH thyroid stimulating hormone; ULN upper limit of normal

**5.4.9. Renal irAEs**

Rule out non-inflammatory causes. If non-inflammatory cause is identified, treat accordingly and continue therapy per protocol.

**Table 5-6. Renal irAE Management Algorithm**

Renal irAEs		
CTCAE Grade of Creatinine Elevation	Management	Follow Up
Grade 1 Creatinine > ULN and > baseline but $\leq 1.5 \times$ baseline	Continue GS-4224 therapy per protocol. Monitor creatinine weekly.	If returns to baseline: Resume routine creatinine monitoring per protocol. If worsens: Treat as Grade 2 or Grade 3-4.
Grade 2-3 Creatinine > $1.5 \times$ baseline to $\leq 6 \times$ ULN	Interrupt GS-4224 therapy per protocol Monitor creatinine every 2-3 days 0.5-1.0 mg/kg/day methylprednisolone IV or oral equivalent Consider renal biopsy	If returns to Grade 1: Taper corticosteroids over $\geq 1$ month, consider prophylactic antibiotics for opportunistic infections, and resume GS-4224 therapy and routine creatinine monitoring per protocol. If elevations persist > 7 days or worsen: Treat as Grade 4.
Grade 4 Creatinine > $6 \times$ ULN	Discontinue GS-4224 therapy per protocol Monitor creatinine daily 1.0-2.0 mg/kg/day methylprednisolone IV or IV equivalent Consult nephrologist Consider renal biopsy	If returns to Grade 1: Taper corticosteroids over $\geq 1$ month and add prophylactic antibiotics for opportunistic infections.

CTCAE Common Terminology Criteria for Adverse Events; irAE immune related adverse event; IV intravenous(ly); ULN upper limit of normal

**5.4.10. Neurological irAEs**

Rule out non-inflammatory causes. If non-inflammatory cause is identified, treat accordingly and continue therapy per protocol.

**Table 5-7. Neurological irAE Management Algorithm**

Neurological irAEs		
CTCAE Grade of Neurological Toxicity	Management	Follow Up
Grade 1 Asymptomatic or mild symptoms; intervention not indicated.	Continue GS-4224 therapy per protocol	Continue to monitor subject If worsens: Treat as Grade 2 or Grade 3-4
Grade 2 Moderate symptoms; limiting instrumental ADL.	Interrupt GS-4224 therapy per protocol Treat symptoms per local guidelines Consider 0.5-1.0 mg/kg/day methylprednisolone IV or oral equivalent	If returns to baseline: Resume GS-4224 therapy per protocol If worsens: Treat as Grade 3-4
Grade 3-4 Severe symptoms; limiting self-care ADL; life-threatening	Discontinue GS-4224 therapy per protocol Obtain neurology consult Treat symptoms per local guidelines 1.0-2.0 mg/kg/day methylprednisolone IV or IV equivalent Add prophylactic antibiotics for opportunistic infections	If improves to Grade 2: Taper corticosteroids over $\geq 1$ month If worsens or atypical presentation: Consider IV immunoglobulin or other immunosuppressive therapies per local guidelines

ADL activities of daily living; CTCAE Common Terminology Criteria for Adverse Events; irAE immune related adverse event; IV intravenous(ly)

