#### **DLT Definition**

A DLT is any toxicity defined below excluding toxicities clearly related to disease progression or disease-related processes occurring during the DLT assessment window (Day 1 through Day 21):

- Grade  $\geq 4$  neutropenia (absolute neutrophil count [ANC]  $< 500/\text{mm}^3$ )
- Grade  $\geq 3$  neutropenia (ANC  $< 1000/\text{mm}^3$ ) with fever (a single temperature of  $> 38.3^\circ\text{C}$  or a sustained temperature of  $\geq 38^\circ\text{C}$  for more than 1 hour)
- Grade  $\geq 3$  thrombocytopenia
- Grade  $\geq 2$  bleeding (eg, gastrointestinal [GI], respiratory, epistaxis, or purpura)
- Grade  $\geq 3$  anemia
- Grade  $\geq 3$  or higher non-hematologic toxicity, except:
  - Grade 3 nausea or emesis with maximum duration of 48 hours on adequate medical therapy
  - Grade 3 diarrhea which persists for  $< 72$  hours in the absence of maximal medical therapy.
- Grade  $\geq 2$  non-hematologic treatment-emergent adverse event (TEAE) that in the opinion of the investigator is of potential clinical significance such that further dose escalation would expose subjects to unacceptable risk

- 
- Continuous treatment interruption of  $\geq 7$  days due to unresolved toxicity
  - Any toxicity event that precludes further administration of GS-4224
  - Any Grade 3 or Grade 4 elevation in aspartate aminotransferase (AST) or alanine transaminase (ALT) associated with a Grade 2 elevation in bilirubin lasting  $\geq 7$  days
  - An immune-related adverse event (irAE, defined as AEs of unknown etiology that were consistent with an immune phenomenon primarily involving the GI tract and the skin, and were considered causally related to drug exposure by investigators) for which immunotherapy should be permanently discontinued (eg, any grade encephalitis, Grade 3 myocarditis, reoccurrence of the same Grade 3 adverse reaction).

[figure not shown]
For certain toxicities, such as laboratory assessments without a clear clinical correlate, a discussion between the investigator and medical monitor may take place to determine if this AE should be assessed as a DLT.

Excluded from this definition:

- Grade 3 AEs of tumor flare (defined as local pain, irritation, or rash localized at sites of known or suspected tumor)
- Grade 3 rash without systemic signs or symptoms
- Grade 3 irAE that resolves to a Grade 1 or less within 21 days except as described above.

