## **1.5. Risk/Benefit Assessment for the Study**

Potential risks of a participant's study involvement include immune-related adverse events (irAEs) (defined as adverse events [AEs] of unknown etiology that were consistent with an immune phenomenon primarily involving the gastrointestinal [GI] tract and the skin, and were considered causally related to drug exposure by investigators) described with other anti-PD-1/PD-L1 agents, unknown AEs, general risks associated with frequent clinic visits and laboratory blood draws, and the associated pain and discomfort of phlebotomy. Strategies to mitigate these risks include close monitoring of lab values as well as AEs. Parameters for discontinuation of the study drug are defined in Section 6.10.1.

There may be no direct benefit to subjects participating in this study; however, data from this study will support the development of GS-4224 for the treatment in subjects with advanced solid tumors. Potential benefits may include the participant's contribution to understanding the safety, tolerability, efficacy, pharmacodynamics, and PK of multiple and escalating doses of GS-4224.

Based on available information, the benefit/risk balance for this study is considered positive.

During a pandemic, additional potential risks to subjects may include adequate study drug availability, interruptions to the study visit schedule, and adherence to protocol-specified safety monitoring or laboratory assessments. Refer to [Appendix 8](#) for further details on the risks and risk mitigation strategy.

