#### 3.2.1.1. DLT Definition

A DLT is any toxicity defined below excluding toxicities clearly related to disease progression or disease-related processes occurring during the DLT assessment window (Day 1 through Day 21):

- Grade  $\geq$  4 neutropenia (absolute neutrophil count [ANC]  $<$  500/mm^3)
- Grade  $\geq$  3 neutropenia (ANC  $<$  1000/mm^3) with fever (a single temperature of  $>$  38.3°C or a sustained temperature of  $\geq$  38°C for more than 1 hour)
- Grade  $\geq$  3 thrombocytopenia
- Grade  $\geq$  2 bleeding (eg, GI, respiratory, epistaxis, or purpura)
- Grade  $\geq$  3 anemia
- Grade  $\geq$  3 or higher non-hematologic toxicity, except:
  - Grade 3 nausea or emesis with maximum duration of 48 hours on adequate medical therapy
  - Grade 3 diarrhea which persists for  $<$  72 hours in the absence of maximal medical therapy.
- Grade  $\geq$  2 non-hematologic TEAE that in the opinion of the investigator is of potential clinical significance such that further dose escalation would expose subjects to unacceptable risk
- Continuous treatment interruption of  $\geq$  7 days due to unresolved toxicity
- Any toxicity event that precludes further administration of GS-4224

- Any Grade 3 or Grade 4 elevation in aspartate aminotransferase (AST) or alanine aminotransferase (ALT) associated with a Grade 2 elevation in bilirubin lasting  $\geq 7$  days
- An irAE for which immunotherapy should be permanently discontinued (eg, any grade encephalitis, Grade 3 myocarditis, reoccurrence of the same Grade 3 adverse reaction).

For certain toxicities, such as laboratory assessments without a clear clinical correlate, a discussion between the investigator and medical monitor may take place to determine if this AE should be assessed as a DLT.

Excluded from this definition:

- Grade 3 AEs of tumor flare (defined as local pain, irritation, or rash localized at sites of known or suspected tumor)
- Grade 3 rash without systemic signs or symptoms
- Grade 3 irAE that resolves to a Grade 1 or less within 21 days, except as described above.

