### 3.5. Study Discontinuation Criteria

The entire study may be discontinued in the event of any of the following:

- New information leading to unfavorable risk-benefit judgment of GS-4224
- Sponsor's decision
- Poor enrollment of subjects, making completion of the study within an acceptable timeframe unlikely
- Discontinuation of development of GS-4224

Health authorities and independent ethics committees (IECs)/institutional review boards (IRBs) will be informed about study discontinuation in accordance with applicable regulations.

The entire study may be terminated or suspended upon request of health authorities.

Recruitment at a center may be stopped for reason that may include low recruitment, protocol violation, or inadequate data recording quality control and quality assurance.

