### 6.10. Criteria for Discontinuation from Treatment or Study

#### 6.10.1. Criteria for Discontinuation from Treatment

Treatment with GS-4224 should be discontinued if any of the following occur:

- Occurrence of an event that would have been considered an exclusion criterion prior to enrollment, that is clinically relevant and affects the subject's safety, and if discontinuation is considered necessary by the investigator and/or sponsor.
- Disease progression, defined by RECIST v1.1 or Lugano 2014 response criteria for cHL as defined in Section 6.6, unless the subject is considered to derive clinical benefit from the treatment by the investigator, is clinically stable, and there is agreement with the sponsor.
- Occurrence of any condition that fulfills criteria for permanent treatment discontinuation, as defined in Section 3.5
- Unacceptable toxicity, or toxicity that, in the judgment of the investigator, compromises the ability to continue study-specific procedures or is considered to not be in the subject's best interest
- Pregnancy during the study; refer to [Appendix 5](#)
- Use of a non-permitted concomitant and/or prohibited medication, as defined in Sections 5.5.1 and 5.5.3, in which the predefined consequence is withdrawal from study drug (sponsor may be contacted to discuss whether study drug must be discontinued).
- Subject Noncompliance
- Intercurrent illness that would, in the judgment of the investigator, affect assessments of clinical status to a significant degree.
- Subject request to discontinue for any reason

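### The DLT definition treats any-grade encephalitis as a reason to end immunotherapy for good, but Table 5-7 has no encephalitis exception and resumes GS-4224 once a Grade 2 event returns to baseline

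*Protocol*

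**What the plan says.** **DLT definition (Protocol 3.2.1.1; same criterion in the synopsis).** One criterion is an irAE for which "immunotherapy should be permanently discontinued (eg, any grade encephalitis, Grade 3 myocarditis, reoccurrence of the same Grade 3 adverse reaction"). Encephalitis is the only one of the three examples that carries the words any grade.

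**irAE management (Protocol 5.4.3 and 5.4.10).** Section 5.4.3 lists encephalitis among the irAEs to watch for and says algorithms exist for several groups, neurological among them. Table 5-7 is the neurological algorithm and works by grade alone:

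- Grade 1, described as "Asymptomatic or mild symptoms; intervention not indicated": "Continue GS-4224 therapy per protocol".
- Grade 2: interrupt GS-4224; if the event returns to baseline, "Resume GS-4224 therapy per protocol".
- Grade 3-4: discontinue.

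The sentence introducing the table sets aside only non-inflammatory causes.

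**Stopping rules.** Section 1.5 states: "Parameters for discontinuation of the study drug are defined in Section 6.10.1". That section has one bullet on permanent discontinuation, triggered by "any condition that fulfills criteria for permanent treatment discontinuation, as defined in Section 3.5". Section 3.5 begins "The entire study may be discontinued in the event of any of the following". The synopsis Treatment paragraph also sends the reader to Section 3.5 for further reasons to stop treatment.

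**The concern.** The DLT text assumes that a subject with immune-related encephalitis of any grade will not receive immunotherapy again. The table a site would open when the event occurs says otherwise below Grade 3. A site following Table 5-7 as written would return a subject to GS-4224 after a resolved Grade 2 event that the protocol elsewhere uses to illustrate a permanent stop.

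Subject safety is at stake, not an estimate or a test. Section 5.4.3 says irAEs can appear at any time from shortly after the first dose, so the table can apply throughout treatment and not only in the 21-day DLT window. Phase 2 was never opened, but SAP Section 1 says that subjects already on study go on being treated and/or followed.

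**Working it through.** No arithmetic beyond counting applies, so the check sets the texts side by side and then looks for any rule that overrides the table.

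**Step 1. Compare by grade.**

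| Grade of encephalitis | Implied by the DLT example | Table 5-7 | Agree? |
|---|---|---|---|
| 1 | permanent stop | continue | no |
| 2 | permanent stop | interrupt, resume at baseline | no |
| 3-4 | permanent stop | discontinue | yes |

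Two of the three rows differ, but they do not carry equal weight. The Grade 1 row covers only events that need no intervention, so few encephalitis cases would be expected to fall there. The Grade 2 row is where the table gives a definite instruction to restart.

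**Step 2. Does the table or its introduction exempt encephalitis?** No row, footnote or lead-in names it. The protocol does write event-specific overrides elsewhere. Section 5.4.2 requires discontinuation for suspected SJS or TEN. The Grade 2 row of Table 5-4 requires it when transaminase and bilirubin rises occur together. Table 5-7 has no equivalent.

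**Step 3. Follow the words per protocol in the table to the stopping rules.**

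- Section 1.5 points to Section 6.10.1, which has 9 bullets. None names encephalitis or any other irAE, and none of the 3 examples in 3.2.1.1 appears there.
- The 1 bullet on permanent discontinuation points to Section 3.5.
- Section 3.5 lists 4 criteria: new risk-benefit information, sponsor decision, poor enrollment, and end of development. None is a subject-level toxicity rule (0 of 4).

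The chain therefore ends without an instruction for an individual subject.

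**Step 4. List what could still stop the drug.**

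- The unacceptable-toxicity bullet of 6.10.1, also reflected in Section 3.4.
- The first bullet of 6.10.1, on events that would have been exclusion criteria, where the investigator and/or sponsor thinks stopping necessary.
- Investigator judgment under the last bullet of 5.4.2, which concerns interruption.
- ASCO or local guidelines (5.5.2) and the individual stopping rules assigned to the SRT Charter (3.2.3).

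The first three are general or discretionary. The last two are outside the documents, so what they say about encephalitis cannot be checked.

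**Step 5. Is the analysis affected?** DLT classification follows 3.2.1.1 whatever Table 5-7 says. A Grade 2 immune-related encephalitis on Day 10, for example, meets the DLT criterion, while the table would have the site restart drug on recovery. The delayed DLT-type event rule in 3.2.1 and the summaries in SAP 7.1.7 use the same criteria and do not change.

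**The case against.** The strongest reply is that the two texts do different jobs. Section 3.2.1.1 decides what counts as a DLT in Days 1 to 21, and encephalitis appears there only as a parenthetical example. Section 5.4.3 presents the algorithms as help for investigators, Section 5.5.2 calls them guidance and sends sites to ASCO or local practice, and the dosing lines in Table 5-7 defer to the rest of the protocol. An irAE that should end immunotherapy fits naturally under unacceptable toxicity, a criterion that stands on its own in 6.10.1. On this view a careful investigator would stop the drug anyway.

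Much of this stands. The DLT text is not a dosing instruction, the table is assistive, and a route to stopping exists. What does not follow is that the texts are consistent. The DLT criterion presupposes a permanent stop, no dosing section carries that stop for Grade 1-2 encephalitis, and the table's written default after Grade 2 is to restart. Section 5.5.2 also sends the reader back to these same algorithms.

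A reader might infer two stronger things. One is that the protocol compels re-dosing after encephalitis. It does not, given the unacceptable-toxicity criterion and investigator judgment. The other is that the mismatch distorts DLT counts or the MTD. It does not, because DLTs are classified from 3.2.1.1 alone.

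**Conclusion.** The inconsistency is real and should be fixed. It is confined to Grades 1 and 2 of one event type; resumption after Grade 2 is its core and the Grade 1 row a minor part. It is aggravated by a cross-reference in 6.10.1 that leads to whole-study criteria, so no rule in the documents expressly requires a stop for Grade 1-2 encephalitis.

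The conclusion rests on two assumptions. The first is that immune-related encephalitis would be managed under Table 5-7. That is an inference, since the table does not name it, but this is the only neurological algorithm. The second is that encephalitis can be graded below 3. Appendix 4 only links to CTCAE, so the grading cannot be checked here, although the any-grade wording in 3.2.1.1 itself allows for lower grades.

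The text mismatch is certain. Its practical effect is not: no encephalitis rate is given, only Phase 1b subjects are exposed, and the guidelines and Charter may cover the case. No claim is made that any subject was or would be harmed.

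**What to change.** Three text changes to the protocol:

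1. **Table 5-7.** Add the line: *Immune-related encephalitis, any grade: permanently discontinue GS-4224.*
2. **Section 6.10.1.** Replace the pointer to Section 3.5 with a subject-level criterion: an irAE that calls for a permanent end to immunotherapy, with any-grade encephalitis, Grade 3 or higher myocarditis, and recurrence of the same Grade 3 irAE as examples. The words *or higher* deliberately extend 3.2.1.1, which says Grade 3, for safety. The recurrence item must be limited to irAEs; without that limit it would clash with Section 5.4.2, which tells sites not to interrupt for Grade 3 or higher fatigue and does not require interruption for Grade 3 lymphopenia.
3. **Synopsis, Treatment paragraph.** Redirect the reference for other stopping reasons from Section 3.5 to Section 6.10.1.

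The cost is one added line, one reworded bullet and one corrected cross-reference. No data, visits or subjects are added. The SAP needs no change.
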